2.1 Eligibility Assessment and Informed Consent

For patients who appear eligible for the study following a “standard-care” or preliminary examination, the study will be discussed with the child’s parent(s) or guardian(s). Parent(s) or guardian(s) who express an interest in the study will be given a copy of the informed consent form to read. Written informed consent must be obtained from the parent or guardian prior to performing any study-specific procedures that are not part of the patient’s routine care.

2.2 Eligibility and Exclusion Criteria

1. Age 3 to < 10 years
2. Amblyopia associated with strabismus (comitant or incomitant), anisometropia, or both
 - Criteria for strabismus: At least one of the following criteria must be met
 - Heterotropia at distance and/or near fixation on examination (with or without spectacles)
 - History of strabismus surgery (or botulinum)
 - Documented history of strabismus which is no longer present (and which, in the judgment of the investigator, is the cause of amblyopia)
 - Criteria for anisometropia: At least one of the following criteria must be met:
 - ≥ 0.50 D difference between eyes in spherical equivalent
 - ≥ 1.50 D difference between eyes in astigmatism in any meridian
3. Visual acuity, measured using the ATS single-surround HOTV protocol for patients aged < 7 years and the E-ETDRS protocol for patients 7 to < 10 years using the Electronic Visual Acuity Tester (the protocol for conducting the visual acuity testing is described in the *ATS Visual Acuity Testing Procedures Manual*), meeting the following criteria:
 - Best-corrected visual acuity in the amblyopic eye 20/40 to 20/80 inclusive (71 to 54 letters inclusive)
 - Best-corrected visual acuity in the sound eye $\geq 20/40$ (≥ 69 letters)
 - Inter-eye acuity difference ≥ 3 logMAR lines (i.e., amblyopic eye acuity at least 3 lines by ATS-HOTV or at least 15 letters by E-ETDRS worse than sound eye acuity)
4. No amblyopia treatment other than spectacles in the past 6 months.
 - Any treatment more than 6 months prior to enrollment is acceptable
5. Spectacles must be worn currently
6. Spectacle correction for measurement of enrollment VA must meet the following criteria and be based on a cycloplegic refraction (using cyclopentolate 1%) that is no more than 6 months prior to enrollment:
 - a. Requirements for spectacle correction:
 - Spherical equivalent must be within 0.50 D of fully correcting the anisometropia
 - Hypermetropia must not be undercorrected by more than +1.50 D spherical equivalent, and reduction in plus must be symmetric in the two eyes

- 327 • Cylinder power in both eyes must be within 0.50 D of fully correcting the
- 328 astigmatism
- 329 • Cylinder axis in the spectacle lenses in both eyes must be within 6 degrees of
- 330 the axis of the cycloplegic refraction when cylinder power is ≥ 1.00 D
- 331 • Myopia of the amblyopic eye greater than 0.50 D by spherical equivalent must
- 332 be corrected, and the glasses must not undercorrect the myopia by more than
- 333 0.25 D or overcorrect it by more than 0.50 D.

334

335 b. Spectacles meeting above criteria must be worn either:

- 336 1) for 16 weeks immediately prior to enrollment, or
- 337
- 338 2) until visual acuity in amblyopic eye is stable (defined as two consecutive visual
- 339 acuity measurements by the same testing method at least 4 weeks apart with no
- 340 improvement of one logMAR line or more)
 - 341 • An acuity measurement done any of the following ways may be considered
 - 342 the first of two consecutive measurements: 1) in current glasses, 2) in trial
 - 343 frames with full correction of hypermetropia with cycloplegia, or 3) by having
 - 344 the patient return in new glasses for first measurement. *Note: since this*
 - 345 *determination is a pre-study procedure, the method of measuring visual acuity*
 - 346 *is not mandated.*

347

348 7. No current vision therapy or orthoptics

349 8. No ocular cause for reduced visual acuity

350 9. Cycloplegic refraction within 6 months prior to enrollment

351 10. Ocular examination within 6 months prior to enrollment

352 11. No myopia more than -6.00 D spherical equivalent in either eye

353 12. No prior intraocular or refractive surgery

354 13. No known skin reactions to patch or bandage adhesives

355 14. Parent has home phone (or access to phone) and is willing to be contacted by the Jaeb Center.

356 15. Parent does not anticipate relocation outside area of an active ATS site within the next 6

357 months

358 16. Parent understands protocol and, if child is eligible to enter randomized trial, parent is willing

359 to accept randomized treatment

360

361 **2.3 Historical Information**

362 Historical information elicited will include the following: date of birth, gender, ethnicity, prior

363 amblyopia therapy (e.g., glasses, patching, pharmacologic, filters), spectacle correction, and

364 history of allergy to bandage adhesive.

365

366 **2.4 Clinical Testing for Enrollment**

367 Examination procedures include:

- 368 1. Measurement of visual acuity in each eye (right eye first) by the ATS single-surround HOTV
369 for patients aged < 7 years and the E-ETDRS testing protocol for patients 7 to < 10 years
370 using the Electronic Visual Acuity Tester. Aspects of the testing protocol that are specific to
371 this study are indicated below:
- 372 • Testing must be done without cycloplegia (with spectacles) no more than 7 days prior to
373 randomization.
 - 374 • Since the patient needs to be wearing spectacles that provide best visual acuity to be
375 enrolled, trial frames/phoropter with a different correction cannot be used to measure
376 acuity at enrollment.
 - 377 • If the patient has difficulty with the acuity testing, often he or she will perform better
378 when the testing is repeated. At the investigator's discretion, acuity can be retested on
379 the same or a subsequent day to assess eligibility.
- 380 2. Ocular motility examination
- 381 • Measurement of predominant alignment by Simultaneous Prism and Cover Test (SPCT)
382 in primary position at distance and near
 - 383 • If performed within prior 7 days, does not need to be repeated at time of enrollment
- 384 3. Ocular examination as per investigator's clinical routine to rule out a cause for reduced visual
385 acuity other than amblyopia.
- 386 • If performed within prior 6 months, does not need to be repeated at time of enrollment.
- 387 4. Cycloplegic refraction using cyclopentolate 1% as per investigator's usual routine.
- 388 • If performed within prior 6 months, do not need to repeat at time of enrollment
- 389 5. Stereoacuity testing (prior to cycloplegia): Titmus fly, Randot Preschool Stereoacuity test
- 390 6. Fixation preference measured (prior to cycloplegia) by the PEDIG fixation preference test,
391 according to the methods outlined in the *ATS Miscellaneous Testing Procedures Manual* and
392 in the following manner:
- 393 • Without a Bangerter filter
 - 394 • With a Bangerter filter. The filter density is selected based on visual acuity of the
395 amblyopic eye (0.3 for 20/40 to 20/63 (71 to 58 letters) and 0.2 for 20/80 (54 to 57
396 letters)). The appropriate density filter trimmed roughly to the size of the average child's
397 lens should be applied to the inner surface of the spectacle lens over the sound eye. This
398 filter must be removed and may be used for measuring fixation preference in subsequent
399 patients as long as it is stored on its original paper backing and remains clean. The filter
400 is applied for the fixation preference test according to methods outlined in the *Bangerter*
401 *application (short-term)* section of the *Bangerter Filter Application Procedures Manual*
402 – This filter must not remain on spectacles following randomization (i.e., this filter must
403 not go home with the child).
- 404 7. Measurement of visual acuity in the sound eye with a Bangerter filter (*see #6 above*) by the
405 ATS single-surround HOTV for patients aged < 7 years and the E-ETDRS testing protocol
406 for patients 7 to < 10 years using the Electronic Visual Acuity Tester.

408 **2.5 Randomization of Eligible Patients**

409 Once a patient is randomized, that patient will be included in the data analysis regardless of
410 whether the assigned treatment is received or not. Thus, the investigator must not randomize a
411 patient until he/she is convinced that the parent/guardian will accept either of the treatment
412 regimens.

413 Treatment must commence within 72 hours following randomization; therefore, a patient should
414 not be randomized until both the investigator and parent are ready to start treatment.

415 The Jaeb Center will construct a Master Randomization List using a permuted block design
416 stratified by site and age (3 to < 7 years, 7 to < 10 years), which will specify the order of
417 treatment group assignments. A patient is officially enrolled when the website randomization
418 process is completed.

419

420 **2.5.1 Randomization Groups**

421 Each patient will be randomly assigned to one of two treatment groups:

422

423 1. 2 hours of daily patching combined with 1 hour of near visual activities while patching

424 2. Bangerter filter worn on sound eye spectacle lens full time (0.3 density for 20/40-20/63
425 (71 to 58 letters) and 0.2 density for 20/80 (54 to 57 letters)) combined with 1 hour of
426 near visual activities.

427

428 **2.5.2 Delay in Randomization**

429 Distance visual acuity testing must be performed within 7 days prior to randomization. If patient
430 randomization is delayed beyond 7 days, the distance visual acuity testing must be repeated to
431 confirm eligibility and establish the baseline acuity for the study.

432 The ocular motility examination must be performed within 7 days prior to randomization. If
433 patient randomization is delayed beyond 7 days, the ocular motility examination must be
434 repeated.

435 No other parts of the examination (including the refraction) need to be repeated if they were
436 performed within 6 months prior to randomization.

437

438 **2.5.3 Bangerter Application**

439 The Bangerter filter must be applied according to the methods for *Bangerter application (long-*
440 *term)* outlined in the *Bangerter Filter Application Procedures Manual*.

441

442 **2.5.4 Assessment of Reading Ability**

443 Reading ability will be assessed binocularly prior to cycloplegia using the Grade-Level Reading
444 Assessment Test in patients randomized to the Bangerter group after applying the Bangerter
445 filter to the sound eye in patients aged 7 to <10 years. The patient may hold the reading card at
446 any distance he or she finds comfortable.

447 Patients who (1) are unable to read the grade-appropriate sized print with the Bangerter filter
448 over the sound eye and (2) will be attending school while on treatment will be prescribed
449 separate glasses (single vision spectacles without Bangerter filter) to use for desk (near) work in
450 school and home (paid for by the study). The time the patient wears the single vision spectacles
451 without the Bangerter filter will be monitored by the parent.

CHAPTER 3: FOLLOW-UP AND TREATMENT

3.1 Treatment Groups

Each patient will be randomly assigned to one of two treatment groups:

1. 2 hours of daily patching combined with 1 hour of near visual activities while patching
2. Bangerter filter worn on sound eye spectacle lens full time (0.3 density for 20/40-20/63 (71 to 58 letters) and 0.2 density for 20/80 (54 to 57 letters)) combined with 1 hour of near visual activities.

Spectacle wear will be continued as prescribed.

An instruction sheet specific to the randomized treatment group will be given to the parent at the time of randomization. This instruction sheet will explain the treatment to which the patient has been randomized and will include instructions for applying the patch and the Bangerter filter.

A calendar specific to the randomized treatment group will be given to the parent at the time of randomization. The parents will be instructed to record the total time the patch or the Bangerter filter was worn each day. Parents of children in the Bangerter group that receive glasses without the filter for school work will be instructed to record the total time the glasses without the filter are worn each day.

3.2 Near Visual Activities

For both treatment groups, the parent will be instructed to have their child spend 1 hour each day doing eye-hand coordination activities at near. For children in the patching group, this 1 hour must be during the period of time they are patched. For children in the Bangerter filter group, this may be performed at any time during the day while the child is wearing his/her spectacles and Bangerter filter.

An instruction sheet will be given to the parent which will indicate the types of near visual activities the child should do. Examples of activities include crafts, coloring, tracing, cutting out objects, blocks, Lego blocks, marbles, dominoes, card games, board games, puzzles, written homework assignments, sorting or stringing beads, reading, writing, activity books, dot-to-dot connecting, hidden pictures, word finds, and computer or video games (e. g., Game Boy/Nintendo/ PlayStation).

3.3 Follow-up Visit Schedule

All patients will have the following study visits after randomization:

- Visit A: 6 weeks \pm 2 weeks
- Visit B: 12 weeks \pm 2 weeks
- Visit C: 18 weeks \pm 2 weeks
- Visit D: 24 weeks \pm 2 weeks

Additional visits can be performed at the discretion of the investigator. A Follow-up Examination Form should be completed on the study website for every exam (not just the minimum required exams).

3.4 Testing Procedures

The following testing will be performed at follow-up visits:

- 500 1. Measurement of sound eye visual acuity through the filter for patients in the
501 Bangerter group by the ATS single-surround HOTV protocol for patients aged < 7
502 years and the E-ETDRS protocol for patients 7 < 10 years using the Electronic Visual
503 Acuity Tester. The same visual acuity protocol used at baseline must be used for all
504 subsequent exams (e.g., if a patient is tested with the HOTV protocol at the baseline
505 exam, visual acuity must be measured by the HOTV protocol on all subsequent
506 exams whether or not the patient is 7 years or older at subsequent exams.)
507 2. Measurement of visual acuity in each eye (right eye first) by the same visual acuity
508 testing method described above (*see #1*)
509 • Testing is performed without cycloplegia with spectacles and without the
510 Bangerter filter
511 3. Ocular alignment measured with the SPCT
512 4. Titmus fly and Randot Preschool Stereoacuity test at the 24-week visit only. Testing
513 must be done in spectacles after removal of the Bangerter filter.
514

515 **3.4.1 Visit A: 6 weeks ± 2 weeks**

- 516 • Administration of the Amblyopia Treatment Index (ATI) prior to visual acuity
517 measurement
518 • Assessment of sound eye visual acuity through the Bangerter filter (Bangerter group
519 only)
520 • Assessment of visual acuity in both eyes without filters (spectacles must be cleaned)
521 • Ocular alignment: record alignment measurements by SPCT
522 • Replace Bangerter filter with same intensity filter as worn at enrollment. The filter should
523 be applied according to the methods for *Bangerter application (long-term)* outlined in the
524 *Bangerter Filter Application Procedures Manual*
525

526 **3.4.2 Visit B: 12 weeks ± 2 weeks**

- 527 • Assessment of sound eye visual acuity through the Bangerter filter (Bangerter group
528 only)
529 • Assessment of visual acuity in both eyes without filters and prior to cycloplegia
530 (spectacles must be cleaned). If testing indicates that amblyopia has resolved (amblyopic
531 eye acuity equal to or better than sound eye acuity, i.e., <1 line or <5 letters), treatment
532 will be maintained at the current level.
533 • Ocular alignment by SPCT
534 • Reading test for patients 7 to <10 years old in the Bangerter treatment group who have
535 failed to improve 1 line (5 letters) or more from baseline. For this test, patients must
536 wear a Bangerter filter with the next density increment from what is currently worn (0.2
537 density filter if currently wearing a 0.3 density filter, or 0.1 density filter if currently
538 wearing a 0.2 density filter). The appropriate density filter trimmed roughly to the size of
539 the average child's lens should be applied to the inner surface of the spectacle lens over
540 the sound eye. This filter must be removed and may be used for measuring fixation
541 preference in subsequent patients as long as it is stored on its original paper backing and
542 remains clean. This filter must not remain on spectacles following the reading test (i.e.,
543 this filter must not go home with the child).
544 • Mandatory cycloplegic refraction for all patients (regardless of treatment group) failing to
545 improve 1 line (5 letters) or more from baseline. If current spectacles do not meet the
546 following criteria, new lenses must be prescribed:

- 547 1. Spherical equivalent must be within 0.50 D of fully correcting the
548 anisometropia
549 2. Hypermetropia must not be undercorrected by more than +1.50 D
550 spherical equivalent
551 3. Cylinder power in both eyes must be within 0.50 D of fully
552 correcting the astigmatism
553 4. Cylinder axis in the spectacle lenses in both eyes must be within 6
554 degrees of the axis of the cycloplegic refraction when cylinder power
555 is ≥ 1.00 D
556 5. Myopia must be corrected, and the glasses must not undercorrect the
557 myopia by more than 0.25 D or overcorrect it by more than 0.50 D
- 558 • The cost of this mandatory lens change will be covered by the study.
 - 559 • If a lens change is mandated, the patient is not eligible for increasing
560 treatment until Visit C, and continues treatment as currently prescribed.
 - 561 • Optional lens changes may be made at the discretion of the investigator if the
562 results of the cycloplegic refraction do not mandate a lens change based on the
563 criteria above. The cost of this optional change in lenses will not be covered
564 by the study.
- 565
 - 566 • Increase treatment intensity if no improvement in visual acuity of 1 line (5 letters) or
567 more from baseline (unless a spectacle change is mandated for the patient following the
568 mandatory cycloplegic refraction –*see above*):
 - 569 • For eyes in patching group that have not improved by at least 1 line (5 letters)
570 from baseline, patching will be increased to 6 or more hours per day
 - 571 • For eyes in the Bangerter filter group that have not improved at least 1 line (5
572 letters) from baseline, the filter density will be increased to 0.2 for patients with
573 baseline visual acuity of 20/40 – 20/63 (71 to 58 letters) and increased to 0.1 for
574 patients with baseline visual acuity of 20/80 (54 to 57 letters).
 - 575 • If treatment intensity is increased for patients in the Bangerter filter group and the
576 patient was determined to have problems reading age-appropriate text on the
577 reading test performed at the time of the 12-week study visit, a separate pair of
578 glasses (single vision spectacles without Bangerter filter) for school work will be
579 prescribed for use at desk (near) work in school and home (*as described in section*
580 *2.5.4*).
 - 581 • Replace Bangerter filter with same intensity filter as Visit A if not increasing intensity of
582 treatment. Otherwise, affix increased intensity filter. The filter should be applied
583 according to the methods for *Bangerter application (long-term)* outlined in the *Bangerter*
584 *Filter Application Procedures Manual*.

585 3.4.3 Visit C: 18 weeks \pm 2 weeks

- 587 • Assessment of sound eye visual acuity through Bangerter filter (Bangerter group only)
- 588 • Assessment of visual acuity in both eyes without filters (spectacles must be cleaned). If
589 testing indicates that amblyopia has resolved (amblyopic eye acuity equal to or better
590 than sound eye acuity, i.e., <1 line or <5 letters), treatment will return to the original level
591 of treatment prescribed at randomization.
- 592 • Ocular alignment by SPCT.
- 593 • Increase treatment intensity if no improvement in visual acuity AND no increase of
594 treatment intensity at visit B:

- 595
- 596
- 597
- 598
- 599
- 600
- 601
- 602
- 603
- 604
- 605
- 606
- 607
- 608
- For eyes in patching group that have not improved at least 2 lines (10 letters) from baseline, patching will be increased to 6 or more hours per day.
 - For eyes in the Bangerter filter group that have not improved at least 2 lines (10 letters) from baseline, the filter density will be increased to 0.2 for patients with baseline acuity of 20/40 – 20/63 (71 to 58 letters) and increased to 0.1 for patients with baseline acuity of 20/80 (54 to 57 letters).
 - If treatment intensity is increased, an age appropriate reading test for patients 7 to <10 years old will be performed as in *section 2.5.4* and separate glasses (single vision spectacles without Bangerter filter) for school work prescribed if needed for patients in the Bangerter filter group.
 - Replace Bangerter filter with same intensity filter as Visit B if not increasing intensity of treatment. The filter should be applied according to the methods for Bangerter application (long-term) outlined in the *Bangerter Filter Application Procedures Manual*.

609 **3.4.4 Visit D: 24 weeks ± 2 weeks – Primary Outcome Exam**

- 610
- 611
- 612
- 613
- 614
- 615
- 616
- 617
- 618
- 619
- Administration of the Amblyopia Treatment Index (ATI) prior to visual acuity measurement
 - Assessment of sound eye visual acuity through the Bangerter filter (Bangerter group only)
 - Masked assessment of visual acuity in both eyes without filters (spectacles must be cleaned)
 - Ocular alignment by SPCT
 - Assessment of binocular function by stereoacuity testing:
 - Bangerter filter must be removed
 - Titmus Fly test and Randot Preschool Stereoacuity test

CHAPTER 4: MISCELLANEOUS CONSIDERATIONS

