217 **1.2 Study Objectives**

- 218 • Primary: To evaluate the non-inferiority of Bangerter filters to 2 hours of daily patching as a
219 primary treatment for moderate amblyopia (20/40 – 20/80) in children ages 3 to <10 years.
- 220 • Secondary:
 - 221 ○ To determine the time course of visual improvement with Bangerter filter treatment.
 - 222 ○ To compare patient quality of life, measured by a modified Amblyopia Treatment
223 Index, between patients treated with patching vs. Bangerter filters.
 - 224 ○ To determine whether the degree of blurring of sound eye visual acuity relative to
225 the amblyopic eye visual acuity predicts improvement in acuity.
 - 226 ○ To determine whether fixation preference is predictive of improvement in visual
227 acuity.

228

229 **1.3 Synopsis of Study Design**

230 Major eligibility criteria (see section 2.2 for a complete listing)

- 231 • Age 3 to < 10 years
- 232 • Amblyopia associated with strabismus, anisometropia, or both
- 233 • No ocular cause apparent for reduced visual acuity
- 234 • Visual acuity 20/40 – 20/80 (71 to 54 letters inclusive) in amblyopic eye
- 235 • Visual acuity 20/40 or better (≥ 69 letters) in sound eye
- 236 • Interocular difference ≥ 3 logMAR lines (≥ 15 letters)
- 237 • No amblyopia treatment other than spectacles in last 6 months
- 238 • Currently wearing spectacles
- 239 • Appropriate spectacles have been worn for 16 weeks prior to enrollment or visual acuity
240 documented to be stable
- 241 • No myopia > -6.00 D spherical equivalent in either eye
- 242 • Cycloplegic refraction within 6 months prior to enrollment

243

244 Treatment Groups

245 Patients will be randomized to two treatment groups:

- 246 • 2 hours daily patching of the sound eye plus one hour near activities while patching
- 247 • Bangerter filter worn on sound eye spectacle lens full time (0.3 for 20/40-20/63 and 0.2
248 for 20/80) plus at least one hour near activities

249

250 Sample Size

251 170 patients (85 per group) with moderate amblyopia (20/40 to 20/80)

252

[figure not shown]
253

254 Visit Schedule

[figure not shown]
- 255 • 6 weeks \pm 2 weeks
256 • 12 weeks \pm 2 weeks: Increase intensity of treatment if acuity not improved 1 line (5 letters) or
257 more from baseline (*see section 3.4.2*)
258 • 18 weeks \pm 2 weeks: Increase intensity of treatment if acuity not improved 2 lines (10 letters) or
259 more from baseline and intensity of treatment not increased at 12 week visit (*see section 3.4.3*)

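### Section 3.4.3 (Visit C) gives sites conflicting treatment instructions: one conflict arises in the filter arm only, the other is an escalation lead-in that does not match its own sub-bullets

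*Protocol*

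**What the plan says.** Section 3.4.3 sets treatment at 18 weeks, nominally 6 weeks before the 24-week primary outcome. Four of its instructions matter here.

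- **Resolved amblyopia, both arms.** If the amblyopic eye is equal to or better "than sound eye acuity, i.e., <1 line or <5 letters), treatment will return to the original level" assigned at randomization.
- **Escalation, lead-in.** "Increase treatment intensity if no improvement in visual acuity AND no increase of" treatment intensity at Visit B.
- **Escalation, sub-bullets.** "For eyes in patching group that have not improved at least 2 lines (10 letters) from baseline", patching is increased. "For eyes in the Bangerter filter group that have not improved at least 2 lines (10 letters) from baseline", the filter is made denser.
- **Filter replacement, filter arm only.** "Replace Bangerter filter with same intensity filter as Visit B if not increasing intensity of treatment".

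Two other places serve for comparison. The synopsis (section 1.3) gives the 18-week rule as "Increase intensity of treatment if acuity not improved 2 lines (10 letters) or" more from baseline, provided intensity was not raised at 12 weeks. The corresponding lead-in for Visit B (section 3.4.2) does carry its threshold: "Increase treatment intensity if no improvement in visual acuity of 1 line (5 letters) or" more from baseline.

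**The concern.** These are operating instructions to sites in the current protocol, so they are not a matter left to the analysis plan. They fix the treatment a child receives over the last stretch before the outcome is measured. In a non-inferiority trial the two regimens being compared should be defined without ambiguity.

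There are three problems of unequal weight:

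- **(a)** For an identifiable group of filter-arm children, two bullets prescribe two different filter densities. Patching has no counterpart to the replacement bullet, so this ambiguity exists in one arm only.
- **(b)** The sentence that introduces escalation states a different condition from the bullets it introduces. Sites could apply either.
- **(c)** A child can satisfy both the resolved rule and the under-2-lines bullet, and the text does not say which comes first.

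**Working it through.** No figure in the protocol bears on this point, and the sample size does not depend on it. The check is therefore a comparison of passages, with arithmetic on letters and lines.

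**(a) Resolved amblyopia in the filter arm.** Take a child who gained less than 1 line by Visit B, was escalated there, and has resolved amblyopia at Visit C. Densities are from sections 2.5.1 and 3.4.2.

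| Baseline amblyopic-eye acuity | At randomization | After escalation at Visit B | Visit C by resolved rule | Visit C by replacement bullet |
|---|---|---|---|---|
| 20/40 to 20/63 | 0.3 | 0.2 | 0.3 | 0.2 |
| 20/80 | 0.2 | 0.1 | 0.2 | 0.1 |

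The last two columns differ in both rows. The replacement bullet applies because the child is not being escalated at Visit C: escalation there requires no increase at Visit B. For a child not escalated at Visit B the two columns coincide. In the patching arm only the resolved rule speaks.

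How easily can a child reach this state? Section 2.2 requires "Inter-eye acuity difference ≥ 3 logMAR lines" (15 letters), and resolved means fewer than 5 letters apart. Starting from the minimum of 15 and with an unchanged sound eye, the gap must close by at least 15 − 4 = 11 letters. At most 4 of these can have been gained by Visit B, since otherwise the child would not have been escalated. At least 11 − 4 = 7 letters must then be gained between Visits B and C. That is possible but probably uncommon.

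**(b) Escalation condition.** Take two children not escalated at Visit B.

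- Gain of 1 line from baseline at both Visit B and Visit C. Read as improvement since baseline, the lead-in does not escalate. The sub-bullets and synopsis do, because 1 < 2.
- Gain of 2 lines from baseline at both visits. Read as improvement since the last visit, which the lead-in does not exclude, there is no improvement and the lead-in escalates. The sub-bullets and synopsis do not.

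The document gives no expected 18-week gain, so the size of the overlap can only be illustrated. Assume gain from baseline is normal with mean μ of 1.5 to 3.0 lines and SD σ of 1.5 to 2.0 lines. The share with some gain but less than 2 lines is Φ((2 − μ)/σ) − Φ((0 − μ)/σ).

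- μ = 1.5, σ = 1.5: Φ(0.33) − Φ(−1.00) = 0.631 − 0.159 = 0.472
- μ = 3.0, σ = 1.5: Φ(−0.67) − Φ(−2.00) = 0.2525 − 0.0228 = 0.230

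Over the whole assumed grid the share is about 23% to 47%, and 15% to 26% for gains of 1 to less than 2 lines. Children already escalated at Visit B must be subtracted. These shares count children for whom the two wordings differ, not children who would be treated differently.

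**(c) Both rules met.**

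- Letter scoring (E-ETDRS, age 7 and over): baseline gap 15, largest gain under 10 is 9, so 15 − 9 = 6 letters remain. Resolved needs 4 or fewer, so a sound-eye drop of 6 − 4 = 2 letters is enough.
- Whole-line scoring (HOTV, under 7): baseline gap 3 lines, largest gain under 2 is 1 line, so 2 lines remain. Being less than 1 line apart then needs a sound-eye drop of about 2 lines.

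**The case against.** On (b), the lead-in contains no action of its own. It hands over to two arm-specific bullets that agree with each other and with the synopsis, so a careful site can probably infer the intended rule. This stands, and it makes (b) a drafting fault more than an open contradiction. A reader might infer that (b) makes the arms differ. The text does not support that: the mismatch is the same in both arms, and randomization is stratified by site.

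On (a), the resolved rule is specific and the replacement bullet is a routine refitting instruction repeated at each visit, so the specific rule could be read as prevailing. The section 1.4 flow chart is not shown in the copy reviewed. Its footnote defines resolved amblyopia, so the chart may settle the order. Both points are fair. Even so, the bullet states one condition and no exception, and no text at hand resolves the conflict.

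A reader might also see a safety problem in an unintended dense filter. Section 4.5.3 says denser filters could lower sound-eye acuity, but adds that this is almost always reversible and has not been reported. The density at issue in (a) is also one the protocol already assigned to that child at Visit B.

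Finally, a reader might infer bias in the primary result. Suppose 3% of the filter arm (0.03 × 85 ≈ 2.6 children) were affected by (a), and each shifted by 0.1 logMAR. Both figures are assumptions. The arm mean would move by 0.03 × 0.1 = 0.003 logMAR, against a margin of 0.075.

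**Conclusion.** The section is wrong as written, in a limited way. Conflict (a) is the firmest: two densities for the same child, in one arm only, unresolved by any text available. Conflict (b) is a lead-in that disagrees with its sub-bullets and the synopsis. Its consequence is possible inconsistency between sites, not between arms. Gap (c) is minor, and a small sound-eye drop triggers it only where acuity is scored in letters.

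The number of children affected cannot be derived from the document, and every share shown above rests on assumed gains. Situations (a) and (c) are likely to involve few children. No effect on the primary comparison is shown and none is claimed. The case for acting is that the correction is specific and almost free, and that it removes contradictory treatment instructions shortly before the outcome visit.

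**What to change.** Reconcile five passages: the escalation lead-in, its two sub-bullets, the synopsis entry for 18 weeks, the resolved-amblyopia rule and the filter-replacement bullet. Check the section 1.4 flow chart against the result. The revised text should contain:

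- one escalation condition, with its threshold and reference visit stated in the lead-in as is done for Visit B;
- one stated order of precedence when a child meets both the resolved rule and the escalation bullet;
- a replacement bullet that defers explicitly to whichever rule governs resolved amblyopia.

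Which threshold and which order are right is for the clinical team. The cost is a clarification memo or minor amendment to sites. It needs no new data and no change to the sample size or primary analysis.
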